4.3 Study milestones

The study described in the present protocol will progress through a number of milestones. These milestones include: 1) study development, consisting of Technical Subcommittee (TSC), scientific, ethics, and PLC review; 2) study conduct data management and data analysis; and 3) preparation and release of study reports. Approximate timelines for these milestones are elaborated upon below.

4.3.1 Study development

Development of the current study protocol will proceed through multiple phases, each involving review and submission of revised draft protocols.

4.3.1.1 TSC review

Following the development of this draft (Version 2.0) study protocol by Ventana, it will be presented to the TSC for review in late June 2002. The TSC will review the protocol and suggest any revisions through an interactive process of consultation. Ventana will then prepare and release a newly revised draft (Version 3.0) that will be released to the TSC and the community of Port Colborne in mid- to late July.

4.3.1.2 Scientific review

This revised draft (Version 3.0) will be submitted by the TSC for scientific peer review in mid- to late July. Comments from scientific reviewers will be due in early August to the TSC. The TSC will compile these comments and provide them to Ventana, keeping individual reviewer's comments anonymous. Ventana will then incorporate appropriate comments into its subsequent draft (Version 4.0) protocol.

4.3.1.3 Ethics review

This newly revised protocol (Version 4.0) will be submitted to the ethical review board, for review in mid-August. Comments from the ethical review board are due mid-September. These comments will be incorporated into the final protocol (Version 5.0) to be ready for implementation in mid-September.

4.3.1.4 PLC review

The protocol submitted for ethical review (Version 4.0) will be reviewed by the PLC in mid-August.

4.3.2 Study Conduct, Data Management and Analysis

Study conduct is scheduled to commence mid-September. This phase of the project will involve administration of the health questionnaire and medical testing to a stratified random sample of residents Port Colborne at a central study facility. Data collection is scheduled over a period of two months ending mid-November. Data management will occur concurrently with data collection starting in mid-September and extend one week

beyond study conduct through to late November. Data analysis will occur over the following two weeks commencing in late November and ending in early December.

4.3.3 Study reports

Ventana will prepare preliminary study reports, draft study reports and a final study report. A preliminary report will be made available to the TSC in early December. Following review by the TSC, a draft study report will be prepared for peer scientific review in mid-December. This review will require approximately one month. A revised draft study report then will be prepared based on the comments generated from the scientific review. This revised report will be presented to the TSC, the Port Colborne community and the PLC. Following input from all three of these parties, a final report will be prepared and released during the first quarter of 2003.

4.4 Consent

Informed consent for this study will be obtained prior to the administration of the questionnaire (see Appendix 11.2) The person obtaining consent must inform the respondent of all aspects pertaining to the respondent's participation in the study.

Participants 18 years of age and older will be required to read and sign an Adult Consent Form/Information Sheet (see Appendix 11.2.1) encompassing the administration of both the health questionnaire and medical testing, to participate in the study. Adolescent subjects (12 to 17 years of age) will be asked to read and sign an Adolescent Assent

Form/Information Sheet (see Appendix 11.2.2). Additionally, parents of adolescent subjects will be asked to read and sign a separate Parental or Guardian Consent Form/Information Sheet (see Appendix 11.2.3) to allow the adolescent's participation in the study.

The written Adult Consent Form/Information Sheet, Adolescent Assent Form/Information Sheet, and Parental or Guardian Consent Form/Information Sheet will include the following information:

- A description of the study;
- The purpose(s) of the study;
- Procedures to be followed, including, if applicable, all invasive procedures;
- The participant's obligations/responsibilities;
- All foreseeable risks/benefits and inconveniences to the participant;
- The voluntary nature of the study;
- That consent for study participation may be withdrawn at any time without penalty or loss of benefits to which the respondent is otherwise entitled;
- That records identifying the participant will be kept strictly confidential (see Section 5.5 Confidentiality);
- Contact information to obtain further information about the study (Adult Consent and Parental or Guardian Consent only);
- Foreseeable circumstances, if any, and reasons under which participation may be terminated;
- Expected duration of participation of the individual;

- Approximate number of individuals participating in the entire study;
- Details of compensation for the time and inconvenience of study participation;
- Details of provision of test results to study participants; and
- Details of provision of test results to participant's physician.

The process for obtaining informed consent will be in accordance with all applicable regulatory requirements. The person obtaining consent and the respondent, or the respondent's legally authorized representative, must both sign and date the informed consent and/or assent form before the respondent can participate in the study. The respondent, or the respondent's legally acceptable representative, will receive a copy of the signed and dated form, and the original will be retained in the study records.

4.5 Confidentiality

An Act to support and promote electronic commerce by protecting personal information that is collected, used or disclosed in certain circumstances, by providing for the use of electronic means to communicate or record information or transactions and by amending the Canada Evidence Act, the Statutory Instruments Act and the Statute Revision Act.

During the course of the study, Ventana personnel will collect the study information from the participants. This data will be collected and stored electronically. In compliance with The Statutes of Canada 2000, Bill C-6, (13/04/2000). All records in which the name of a participant appears will be kept confidential and will be provided with a unique identifier. The name will never appear on any forms, report or publication. The statute covers

personal health information with respect to an individual, whether living or deceased meaning:

- information concerning the physical or mental health of the individual;
- information concerning any health service provided to the individual;
- information concerning the donation by the individual of any body part or any bodily substance of the individual or information derived from the testing or examination of a body part or bodily substance of the individual;
- information that is collected in the course of providing health services to the individual; or
- information that is collected incidentally to the provision of health services to the individual.

In addition, Ventana assures that a respondent's personal data will not be used, disclosed, nor collected in any manner incompatible with the intended purpose of the research. Care will be taken to keep the information secure, whether on hard copy, computer or stored electronically. An individual respondent's identity will not be revealed during the course of the study. Unique identifying numbers will be used as an alternative to a personal identity. Once all of the data has been validated, all linkages between the unique identifier and personal identity will be erased. After this point, there will be no method whereby a person's name can be linked with individual, specific health outcomes. Unless otherwise specified, only aggregate data, not individual data, will be published or released to the general public, as with any scientific study.

Participants will be informed of the degree of confidentiality that will be maintained throughout the study during the process of obtaining informed consent.

Research specifications, such as background, objectives, and technical approaches or ideas, provided by Ventana, remain the property of Ventana and the contents will not be revealed to a third party without Ventana's permission or unless instructed by a court of law.

5.0 Data Management

5.1 Data collection and quality control

All data, including the signed informed consent (Adult Consent, Adolescent Assent, Parental or Guardian Consent) will be collected on a two-part NCR document. The informed consent will be provided as a single document for adult consent, parental or guardian consent or adolescent assent. Once written consent has been given, a copy will be retained by the subject, and one by Ventana. The informed consent will be provided with a unique code and inserted into a case report form (CRF) for the study participant. The CRF will be two-part NCR. The top page (white sheet) will be classed as the original document and the second page (yellow sheet) will be classed as the file copy.

At the completion of each questionnaire, the interviewer coordinator will review for completeness. Alongside questions that have not been answered by the study subject, the interviewer will sign their initials. At the bottom of each page, the interviewer will sign

their initials. Each white page will be removed from the CRF upon completion and submitted for data entry.

All data provided on test samples from the laboratory will be provided in electronic format predetermined for compatibility with the central data base. A common unique code will be utilized for each participant.

Data collection by the central laboratory will be done via electronic data capture.

Data from the health test machines will be provided from a print-out that will be used for double entry methodology.

Data from the ECG will be entered into the central data base as descriptive text.

5.2 Data storage

All hard copy (CRF) and electronic data will be stored by Ventana for five years. A copy of all data will be made available to the regional municipality of Niagara Public Health Department. This data will exclude any personal identifiers. All data stored by Ventana will be in compliance with the Personal Information Protection and Electronic Documents Act (January 1, 2002) and Good Clinical Practice.

5.3 Data transfer

All data collected in the CRF will be entered into the central data base by double entry methodology.

5.4 Chain of custody

Chain of custody will be implemented to ensure limited use, limited disclosure and accuracy of all test results. It will also ensure the integrity of all test samples. Original data will be collated in hard copy at the end of each interview session and transferred to a sealed container. All original data will be removed from the central facility in Port Colborne at the end of each day and carried to the Ventana central facility.

All test samples will be shipped in sealed containers via a designated courier to the central laboratory.

All CoCs test containers will be metal-free collection and storage containers. These will be dispatched in a tamper-proof form to the Port Colborne site.

All test samples will be shipped from the Port Colborne facility at the end of each clinical day; samples will not be stored at this facility overnight.

The areas in Port Colborne where test samples are stored prior to dispatch will be with limited access.

6.0 Data Analysis

6.1 Sample Size Calculation

Sample size is an important element that needs to be addressed when designing a health survey. When estimating community rates of a certain characteristic or health condition, random sampling or chance may partly explain the findings. For example, if the overall smoking rate in Port Colborne were 30%, taking repeated samples of 10 individuals would not be expected to result in the finding of three smokers in every sample of 10 individuals. For this reason, a sufficient number of individuals must be sampled so that reasonably accurate estimates of the health characteristics of the community can be obtained.

The term “Power” is used to describe the ability of a study to detect a true difference when making comparisons between two or more groups. If a study has a power of 50%, this means it has a 50-50 chance of detecting this difference. Typically studies aim for a power of at least 80% as it would be unsatisfactory if there was more than 20% chance of missing this difference. The number of participants that are needed to ensure sufficient power are influenced by several factors including: the size of the difference that is to be detected; the prevalence of the disease or characteristic of the population that is being compared, the variance of the characteristic that is being examined; and the size of the Type I error (probability of rejecting the null hypothesis when it is true). Each of these factors must be specified in order to estimate the power of a study.

The Power of a study may also be calculated in order to ensure that the average value of a variable, or prevalence of a health condition within a community, is calculated with sufficient precision. This is referred to as a one-sample statistical test. Alternatively, the objective of the study may be to compare differences in disease rates between two communities. In this case, the study power is calculated to ensure that there are sufficient numbers of participants in both communities so that a meaningful statistical test can be constructed to allow comparisons between two communities. This is referred to as a two-sample test.

6.1.1 Power calculations for the health questionnaire

Power was calculated based on the primary objective of the study which is to characterize the current health of residents in Port Colborne using a comprehensive health assessment questionnaire and medical testing. As mentioned previously, a stratified sampling strategy will be applied to recruit individuals from five geographical areas. The sample size of the Health questionnaire and medical tests was calculated by determining the number of individuals needed to measure the prevalence of selected health conditions with sufficient precision both within the Rodney Street Area, and the remainder of Port Colborne. Specifically, the sample size of 1,000 was selected to ensure that a 5% prevalence of asthma could be measured within an accuracy of 2% 16 times out of 20, and that the prevalence of nickel sensitivity estimated at 9.5% among women could be measured within 7% and 13% 16 times out of 20 (see Table 1 below).

Table 1: Sample Size Needed to Compare Disease Prevalence Rates (Proportions)

Health Condition	Anticipated Prevalence	Prevalence Range Permitted**	Subjects needed in Area 3	Subjects needed in remainder of Port Colborne	Minimally detectable Odds Ratio*
Asthma	5%	4-6%	418	777	2.0
Asthma	5%	3-7%	160	193	3.2
Asthma	5%	4.5%-5.5%	699	2662	1.7
Cancer	0.5%	0.4-0.6%	811	5630	3.4
Nickel Sensitivity (females)	9.5%	8%-11%	370	607	1.8
Nickel Sensitivity (females)	9.5%	7%-13%	181	223	2.4

* Comparison of prevalence of disease between Area 3 and the rest of Port Colborne

**with Power of 80% and an alpha error of 5%

Assuming that there is a response rate of 65%, and that 50% of residents in the region are female, there will be 234 female participants in the Rodney Street area and a remaining 251 female subjects in the rest of Port Colborne. This will enable nickel sensitivity to be measured with sufficient precision as outlined in the table above. Moreover, when supplemented with data obtained from males, there will be sufficient precision to measure the prevalence of asthma within an accuracy of 2% in both sexes (see Table 1). It is important to note that due to the rarity of cancer, the health questionnaire is unable to measure the prevalence of cancer in Port Colborne with sufficient precision. The evaluation of this health outcome will be addressed in a subsequent research protocol.

The estimated number of dwellings and individuals that make up the target population are listed in Table 1. This list is considered approximate as it is based on Canadian census data obtained in 1996.

Table 2: Estimated Number of Households and Individuals 12 years of Age and Older* within Each Sampling Region for the health questionnaire.

Region (EA's)	Number of private dwellings	Estimated population 12 years of age and older
1- West of the Welland Canal, south of Clarence and Augustine Road (151-156)	1,945	4,055
2- West of the Welland Canal, north of Clarence (116-120)	2,260	4,798
3- East of the Canal, south of Durham (includes Durham) and is bounded by Davis and Lake (110)	365	719
4 - East of the Canal, north of Durham (excludes Durham) and is bounded by Snider Road (106,108)	775	2,346
5- Other areas of Port Colborne (101-105,107,109,112-113)	2,030	4,437
Total	7,375	16,355

* assumes that 85% of the Port Colborne community is 12 years of age and older (based on 1996 Census data from Statistics Canada).

It is very important to note that while there are sufficient numbers to measure the prevalence of the selected health conditions with the desired precision, there is limited power to make comparisons between rates in the Rodney Street area to the remainder of Port Colborne. Specifically, with 500 subjects recruited in both the Rodney Street area and other parts of Port Colborne, the study has the power to detect an odds ratio of 2.1 for the comparison of asthma rates between the two regions with a power of 80% and a type I error rate of 5%. The odds ratio of 2.1 corresponds to a greater than two-fold increased prevalence rate in area 3 relative to the rest of Port Colborne. Similarly, for a comparison of nickel sensitivity rates in females between the two regions, there is power to detect an odds ratio of 2.2.

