6.4 Statistical Analysis

The frequency distributions of variables collected within the health questionnaire and medical tests will be tabulated. The number of missing responses for each variable will be presented, and where possible, these missing values will be treated as a separate category. Particular attention will be given to examining response rates for income levels, since this variable will be used as a proxy to socioeconomic status. If necessary, other factors, such as education, may need to be used instead.

Prevalence rates for health conditions will be calculated by age-group for males and females. Statistically significant differences across strata will be evaluated by using the Chi-Square and likelihood ratio tests for categorical data, and the Student's t-test for continuous data. Multivariate analysis of variance will be used to adjust comparisons for the influence of potential confounding variables. Comparisons will need to take into account possible differences in the age and sex structure of the populations being compared. Of particular interest will be the comparison of Area 3 (otherwise known as the Rodney Street area) to the rest of Port Colborne. Comparisons will also be made to reference data for Ontario or other normative data.

To evaluate the potential influence for response bias, where possible, socio-economic characteristics will be compared between non-respondents and participants. These variables will include: age, sex, family size, income level, and neighborhood of residence. Statistical tests of significance will be performed to determine whether non-responders differed from those who participated in the survey. Response bias will also be examined by comparing survey results obtained from the 1996 Canadian census data.

The prevalence of selected health characteristics will be compared to responses obtained from participants of the 2000 CCHS. In order to control for differences in the underlying populations, direct standardization will adjust for the age and gender make-up of the populations being compared. The ratio of these standardized rates will be calculated, and

95% confidence intervals of this ratio will be used to assess statistically significant differences.

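### Table 1's sample sizes are 80% confidence-interval sizes mislabelled as 80% power and 5% alpha, and they rest on populations that contradict Table 2

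*Protocol*

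**What the plan says.** Section 6.1.1 of the protocol gives two precision targets as the reason for choosing 1,000 people. One is that "a 5% prevalence of asthma could be measured within an accuracy of 2% 16 times out of 20"; the other is that "the prevalence of nickel sensitivity estimated at 9.5% among women could be measured within 7% and 13% 16 times out of 20". Both refer to Table 1.

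The rows of Table 1 that carry these targets read "Asthma 5% 3-7% 160 193 3.2" and "Nickel Sensitivity (females) 9.5% 7%-13% 181 223 2.4". The columns are condition, anticipated prevalence, permitted range, subjects needed in Area 3 (the Rodney Street area), subjects needed in the remainder, and minimally detectable odds ratio. A third row used below is "Asthma 5% 4-6% 418 777 2.0". The double-asterisk footnote, attached to the permitted-range column, says "with Power of 80% and an alpha error of 5" percent.

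The same section expects 234 women in Area 3 and 251 elsewhere (65% response, half of residents female) and concludes: "This will enable nickel sensitivity to be measured with sufficient precision as outlined in the table above". Table 2, also in 6.1.1, puts the population aged 12 and over at 719 in Area 3 and 16,355 in total.

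**The concern.** The text and the footnote describe different calculations. Sixteen in twenty is an 80% confidence level. A 5% alpha belongs with a 95% interval or a two-sided 5% test, and power plays no part in a one-sample precision size. A reader cannot tell from the page which basis produced the sizes.

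The table also fails a simple check against Table 2. A size with a finite-population correction can never exceed the population it is corrected to, yet the cancer row needs 811 people in an area with 719 eligible residents.

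At stake is the only written justification for 1,000 participants, and what a reader will believe about the precision of the nickel estimate in women.

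**Working it through.** **Inputs.** From 6.1.1: prevalences 5%, 0.5% and 9.5%; the permitted ranges; 65% response; 50% female; 234 and 251 women. From Table 2: 719 people in Area 3 and 16,355 − 719 = 15,636 elsewhere. Women at 50%: 719 / 2 ≈ 360 and 15,636 / 2 = 7,818.

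**Formula.** n0 = z² p(1−p) / d², then n = n0 / (1 + n0/N).

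**Step 1: reproduce Table 1.** With z = 1.2816 (80% confidence) and N solved back from the table (about 900 and 18,100):

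| Row | d (points) | n0 | Area 3, N = 900 | Stated | Remainder, N = 18,100 | Stated |
|---|---|---|---|---|---|---|
| Asthma 4–6% | 1 | 780.1 | 417.9 | 418 | 748 | 777 |
| Asthma 3–7% | 2 | 195.0 | 160.3 | 160 | 193 | 193 |
| Asthma 4.5–5.5% | 0.5 | 3,120.5 | 698.5 | 699 | 2,662 | 2,662 |
| Cancer | 0.1 | 8,170.8 | 810.7 | 811 | 5,630 | 5,630 |
| Nickel 8–11% | 1.5 | 627.6 | 369.7 | 370 | 607 | 607 |
| Nickel 7–13% | 2.5 | 225.9 | 180.6 | 181 | 223 | 223 |

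Eleven of the twelve sizes match; 777 does not. The women-only rows fit the same N as the rows for both sexes.

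**Step 2: try the footnote's basis on the asthma 3–7% row** (stated 160 / 193), with Table 2 populations.
- 95% confidence: n0 = 456.2, giving 279.1 / 443.2.
- 80% power with 5% alpha, z = 1.96 + 0.84: n0 = 932.1, giving 405.9 / 879.6.

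Neither fits. The odds-ratio column does broadly follow 80% power and two-sided 5%. With continuity correction, the computed values in row order are 2.00, 3.18, 1.64, 3.08, 1.79 and 2.36, against the stated 2.0, 3.2, 1.7, 3.4, 1.8 and 2.4. The cancer row is the poor match.

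**Step 3: compare populations.** About 900 against 719, and about 18,100 against 15,636. Hence 811 required of 719 people, and 370 women required of about 360.

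**Step 4: the 7%–13% row.** The limits lie 2.5 points below and 3.5 above 9.5%. With N = 900 and 18,450 (the all-age population in section 4.1.1), d = 3 would give 134 / 156 and d = 3.5 would give 102 / 115. Only d = 2.5 gives 181 / 223.

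**Step 5: recompute at 80% confidence with Table 2 populations.**
- Asthma ±2: 153.4 / 192.6.
- Asthma ±1: 374.2 / 743.1.
- Nickel ±2.5, women (N = 360 / 7,818): 138.7 / 219.6.

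**Step 6: 95% half-widths at the expected sample.** The half-width is 1.96 √(p(1−p)/n), multiplied by √((N−n)/(N−1)) where the correction is applied. Expected people: 719 × 0.65 = 467 and 2 × 251 = 502.

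| Estimate | n | Without correction | With correction |
|---|---|---|---|
| Asthma, Area 3 | 467 | 1.98 | 1.17 |
| Asthma, remainder | 502 | 1.91 | 1.88 |
| Nickel, women, Area 3 | 234 | 3.76 | 2.22 |
| Nickel, women, remainder | 251 | 3.63 | 3.57 |

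For nickel in the remainder, 9.5 ± 3.57 is 5.9% to 13.1%. In Area 3 the interval is 7.3% to 11.7% with the correction and 5.7% to 13.3% without it.

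**The case against.** The 80% level is disclosed, since both target sentences state it. At that level the claim is true: 234 and 251 women give ±2.46 and ±2.37 points even without the correction, about 7.0%–12.0% and 7.1%–11.9%, inside 7%–13%. Section 6.1 also warns that it uses the word power for one-sample precision. The wrong N errs on the safe side in Area 3 (160 falls to about 154) and hardly moves the target rows elsewhere. The impossible 811 is in the cancer row, which 6.1.1 itself sets aside, and 777 is not in a target row. Sizing nickel on the nearer limit also satisfies the farther one. All of this stands, and it limits the consequence. It does not make the footnote, the populations or the 777 right.

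A reader might infer from the 80% basis that asthma cannot be held within 2 points at 95%. At Table 1's minimum sizes of 160 and 193 the 95% half-widths are indeed about 3.0 and 3.1 points, but the protocol does not plan to stop there. The expected 467 and 502 exceed the 279 and 443 that ±2 at 95% would need.

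A reader might also infer that the protocol promises 95% intervals for each area's prevalence. It does not. In section 6.4, "95% confidence intervals of this ratio will be used to assess statistically significant differences" concerns the ratio of standardized rates against the national health survey, and the other 95% intervals there are for odds ratios. The 95% figures above show what the usual level would give; they do not show that a stated target is missed.

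**Conclusion.** Table 1 is wrong as written in four respects: the basis given for its precision columns, the populations behind them, the entry 777, and a nickel range whose upper limit does not match the 2.5 points used. Neither target row is undersized at the disclosed 80% level, and nothing here shows that 1,000 is too few.

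The one consequence for interpretation is nickel sensitivity in women. At 95% the half-width is about 3.6 points outside Area 3 (5.9%–13.1%). In Area 3 it is 2.2 points with the finite-population correction or 3.8 without.

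These figures assume simple random sampling, the protocol's 65% response and 50% female, and its anticipated prevalences. The protocol gives no design effect for the strata, the selection of one person per household or the weighting. The asthma result at 95% has little room: variance inflation above about 1.02 in Area 3 (without the correction) or about 1.1 in the remainder would take it past 2 points. The populations of about 900 and 18,100 are solved back from the table, which states none. Their source is not established: the all-age 18,450 of section 4.1.1 gives 2,669 and 5,663 where the table has 2,662 and 5,630.

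**What to change.** In section 6.1.1:
- Move the power and alpha footnote to the odds-ratio column.
- Label the range and subjects-needed columns as 80% confidence with a finite-population correction, and state each N.
- Recompute with 719 and 15,636, and with about 360 and 7,818 for the women-only rows. Rounded up, asthma ±2 becomes about 154 / 193 and nickel ±2.5 about 139 / 220.
- Correct 777: about 748 on the table's own method, about 743 with Table 2's population.
- Reconcile the 7%–13% range with the 2.5 points used, in both the table and the text.
- Beside the sentence claiming that precision is sufficient, give the expected 95% half-widths from step 6 and say whether the correction is applied.

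The cost is one table and a few sentences. Enrolment and analysis do not change; the stated precision for nickel becomes less favourable.

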4.1.1 Population

Port Colborne has a population of 18,450. From this population, a sample of 1,000 people who are at least 12 years of age will be randomly selected to participate in the health questionnaire and the medical testing. This sample will be chosen from a listing of all households based on phone numbers.

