6.5.1 Mock Tables

Table 1.
Response Rates, by Sampling Areas,
CHAP Comprehensive Health Questionnaire, Fall 2002

Total Number of Randomly Selected Households
Total Number of Questionnaire Refusals
Refusals from Area 1
Refusals from Area 2
Refusals from Area 3
Refusals from Area 4
Refusals from Area 5
Overall Questionnaire Response Rate
Total Number of Biological Testing Refusals
Refusals from Area 1
Refusals from Area 2
Refusals from Area 3
Refusals from Area 4
Refusals from Area 5
Overall Biological Testing Response Rate

Table 2.
Demographic Characteristics of Participants, by Sampling Areas,
Compared to Census Data
CHAP Comprehensive Health Questionnaire, Fall 2002

Characteristic	Area 3	1996 Census Data for Area 3	Areas 1, 2, 4, 5	1996 Census Data for Areas 1, 2, 4, 5
	N (%)	N (%)	N (%)	N (%)
Sex				
Female				
Male				
Age				
0 - 14				
15 - 19				
20 - 24				
25 - 54				
55 - 64				
65 - 74				
≥ 75				
Mean				
Mean Household Size				
Household Income				
< \$20 000				
\$20 000 to less than 40 000				
\$40 000 to less than 60 000				
\$60 000 to less than 80 000				
≥ \$ 80 000				
Education				
Less than high school				
High School				
Post Secondary				
Ethnic Background				
Caucasian				
Oriental				
Native				
Other				
Marital Status				
Married/Common-law				
Single				
Divorced/Separated				
Widowed				

categorized by standard thresholds

Table 3.
Demographic Characteristics of Participants, by Sampling Areas,
CHAP Comprehensive Health Questionnaire, Fall 2002

Characteristic	Area 3	Areas 1, 2, 4, 5	Total for Port Colborne	p-value [†]
	N (%)	N (%)	N (%)	
Sex				
Female				
Male				
Age				
0 – 14				
15 - 19				
20 - 24				
25 - 54				
55 - 64				
65 - 74				
≥ 75				
Mean				
BMI				
Underweight [‡]				
Average [‡]				
Overweight [‡]				
Obese [‡]				
Mean				
Mean Household Size				
Household Income				
< \$20 000				
\$20 000 to less than 40 000				
\$40 000 to less than 60 000				
\$60 000 to less than 80 000				
≥ \$ 80 000				
Education				
Less than high school				
High School				
Post Secondary				
Ethnic Background				
Caucasian				
Oriental				
Native				
Other				
Marital Status				
Married/Common-law				
Single				
Divorced/Separated				
Widowed				
Years lived in Port Colborne				
< 5				
5 - <10				
10 - <20				
20+				

[†] p-value is based on Chi-square for comparison of proportions, likelihood ratio test for categorical variables and t-test for comparison of means.

[‡] categorized by standard thresholds

Table 4.

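### Mock Table 2 sets a sample aged 12+ beside census data in a 0–14 age band, and the 12+ counts in Section 6.1.1 do not reconcile with the stated population

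*Protocol*

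**What the plan says.** Section 4.1.1 states that "Port Colborne has a population of 18,450", without a year or source, and the inclusion criteria limit entry to people aged 12 or older.

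Table 2 of Section 6.1.1 lists private dwellings and estimated residents aged 12+ for the five sampling areas. Its bottom line is "Total 7,375 16,355". The footnote says the table "assumes that 85% of the Port Colborne community is 12 years of age and older (based on 1996 Census data from Statistics Canada", and the text calls the list approximate. The Area 4 row reads "106,108) 775 2,346". The rows for Areas 1 and 2 read "151-156) 1,945 4,055" and "116-120) 2,260 4,798".

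Mock Table 2 in Section 6.5.1 puts participants beside census columns, one of them headed "1996 Census Data for Areas 1, 2, 4, 5". The first age row is 0–14 for both sample and census. Mock Table 3 uses the same row but has no census column.

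The census comparison has stated uses. The Synopsis relies on it to judge how far results generalize. Section 4.1 calls the assessment of non-response critical and allows further weighting from census data. Section 6.2.1.1 would use demographics to adjust the data, and Section 6.4 lists the census comparison as a check on response bias.

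**The concern.** The two columns of mock Table 2 describe different populations. The sample can fill only ages 12 to 14 of the first row, whereas a census column completed as labelled would hold everyone from birth to 14. Children under 12 would also enter the denominator of every other census age percentage and the census mean age. A sample with no response bias would then look short of young people and too full of everyone else. Because the protocol ties possible re-weighting to this comparison, an artefact of the table layout could lead to a real adjustment.

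The second problem is that the protocol's population figures disagree. Weighting for the Rodney Street oversampling needs stratum sizes, and Table 2 of Section 6.1.1 is the only place that gives them by area. If one area's count is wrong and is carried into the weights, that area's influence on city-wide estimates is wrong too.

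**Working it through.** **Inputs.** Population 18,450 (Section 4.1.1). Share aged 12+ 85%, and dwellings and 12+ residents by area (Table 2 and footnote, Section 6.1.1). Age rows (mock Table 2, Section 6.5.1). About 500 participants each in Area 3 and in the rest (Section 6.1.1).

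**1. The printed total.** 4,055 + 4,798 + 719 + 2,346 + 4,437 = 16,355, and the dwellings sum to 7,375. The table adds up.

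**2. Against the stated population.** 0.85 × 18,450 = 15,682.5, so 16,355 is 672.5 (4.3%) too high. Rounding of the 85% does not explain it: 84.5% to 85.5% gives 15,590 to 15,775. Put the other way, 16,355 / 0.85 = 19,241 residents, and 16,355 / 18,450 = 88.6%.

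**3. People aged 12+ per dwelling.**

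| Area | 12+ / dwellings | Ratio |
|---|---|---|
| 1 | 4,055 / 1,945 | 2.08 |
| 2 | 4,798 / 2,260 | 2.12 |
| 3 | 719 / 365 | 1.97 |
| 4 | 2,346 / 775 | 3.03 |
| 5 | 4,437 / 2,030 | 2.19 |

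The four other areas together have 14,009 / 6,600 = 2.12. At that rate Area 4 would hold about 1,645 people and the total would be about 15,654, within 0.2% of 15,682.5. Working back from 15,682.5, Area 4 would need 15,682.5 − 14,009 = 1,673.5 people, or 2.16 per dwelling.

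**4. Effect on weights, if these counts were used and Area 4's population is the error.**
- Area 4 share: 2,346 / 16,355 = 14.3% as printed, against 1,673.5 / 15,682.5 = 10.7%. The ratio is 1.34. With the pooled-rate figure (1,645 / 15,654 = 10.5%) it is 1.37.
- Area 3 share: 719 / 16,355 = 4.4%, against 719 / 15,682.5 = 4.6%.
- City-wide prevalence, if Area 4 differed from the rest by 5 points: 0.05 × (0.143 − 0.105) ≈ 0.002, or about 0.2 points.

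**5. The age row in mock Table 2.** Assume equal numbers at each single year of age from 0 to 14.
- With 15% under 12, each year of age holds 0.15 / 12 = 1.25% of residents. The all-ages census row is 15 × 1.25% = 18.75%. A representative 12+ sample has 3 × 1.25% / 0.85 = 4.4%. Each band from 15 up is larger in the sample by 1 / 0.85 = 1.18.
- With 11.4% under 12 (taking 88.6% from step 2), the figures are 14.25% against 3.2%, and 1 / 0.886 = 1.13.

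For about 500 participants, the simple-random-sampling standard error around 18.75% is √(0.1875 × 0.8125 / 500) = 1.75 points. The 14.3-point gap is about 8 standard errors. In the second case, 11.0 points over 1.56 is about 7.

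**The case against.** The strongest reply is that the weighting consequence is conjecture. No section names Table 2 of Section 6.1.1 as the source of weights. It sits in the sample-size section and is labelled approximate, and Section 4.1 speaks only of available census data and of formulas to be considered. A reader might infer that the survey weights will be wrong, but the protocol does not support that. Even if the table were used, the only oversampled area is Area 3, whose share barely changes, and the planned mock comparisons pool Area 4 with Areas 1, 2 and 5. This stands, and the weighting effect is stated only conditionally.

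A reader might also infer that the 85% was misapplied, or that Area 4's population is the mistake. Neither is shown. Dividing back, 2,346 / 0.85 = 2,760 and 4,437 / 0.85 = 5,220 exactly, so 85% appears to have been applied area by area. The figure of 18,450 is undated and may belong to another year. Area 4's dwelling count could be the one that is too low: 2,346 / 2.12 = 1,107 dwellings, which would lift the total from 7,375 to 7,707, nearer the 7,856 households in Section 4.1.3. In that case Area 4's 14.3% share would need no correction.

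On the age row, the mock tables are empty shells, and whoever fills in the census column could cut it at 12. But nothing in the protocol says so, and the printed label says otherwise. It would also go too far to call the whole response-bias check wrong. Section 6.4 separately compares participants with non-respondents, which this row does not touch, and the sex and income rows should be little affected.

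**Conclusion.** The age-band fault holds. Filled in as labelled, mock Table 2 would show a representative sample about 11 to 14 points short in its first age row and 13% to 18% too large in the older bands. That range rests on 11.4% to 15% of residents being under 12 and on an even spread of ages 0 to 14. It would be read as age-related response bias and could prompt an unwarranted adjustment.

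The population mismatch also holds. A 12+ total of 16,355 cannot be 85% of 18,450, and Area 4 stands apart from every other area. This points to an error in Area 4's population or dwelling count, or to two different population bases, without proving which. Its effect on weights is conditional and limited: up to about a third on Area 4's share, almost nothing on Area 3's, and about 0.2 points on a city-wide prevalence under the 5-point illustration. Both points should be corrected; neither undermines the design.

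**What to change.** - In mock Table 2, start the age rows at 12 and restrict all census columns, including their denominators and mean age, to residents aged 12+. Where census counts for ages 12 to 14 are not available, compare only ages 15 and over in both columns.
- Relabel the first age row of mock Table 3 as 12–14.
- Give the year and source of 18,450.
- Recheck both Area 4 figures, population and dwellings, against the enumeration-area source, and re-issue Table 2 of Section 6.1.1 on a single population base.
- Name the counts to be used for any weighting, and use the corrected ones.

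The cost is a look-up in the census source and edits to three tables. Sampling and data collection do not change.
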